Serotype	n	PNEUMOSIL (N=247)		Synflorix (N=250)		Treatment group comparison: PNEUMOSIL/Synflorix		
		GMT	(95% CI)	GMT	(95% CI)	GMT Ratio	(95% CI)	
Type 1	247	85.17	(71.34 – 101.69)	249	27.55	(22.96 – 33.06)	3.09	(2.40 – 3.98)*
Type 5	247	161.34	(139.94 – 186.02)	249	115.93	(98.85 – 135.97)	1.39	(1.12 – 1.72)*
Type 6A	247	1317.16	(1109.36 – 1563.88)	241	7.06	(5.83 – 8.56)	186	(144 – 241)*
Type 6B	243	913.52	(745.97 – 1118.70)	245	467.65	(365.27 – 598.73)	1.95	(1.42 – 2.69)*
Type 7F	247	1833.71	(1612.31 – 2085.51)	250	1586.75	(1392.62 – 1807.94)	1.16	(0.96 – 1.39)
Type 9V	242	141.72	(113.36 – 177.16)	249	376.77	(324.01 – 438.13)	0.38	(0.29 – 0.49)*
Type 14	244	1019.34	(816.53 – 1272.52)	247	1102.64	(878.56 – 1383.87)	0.92	(0.67 – 1.27)
Type 19A	247	148.59	(121.35 – 181.95)	236	11.09	(9.19 – 13.39)	13.4	(10.2 – 17.7)*
Type 19F	247	594.27	(509.98 – 692.49)	250	895.39	(784.96 – 1021.35)	0.66	(0.54 – 0.81)*
Type 23F	246	767.24	(648.95 – 907.10)	243	253.09	(197.10 – 325.00)	3.03	(2.25 – 4.09)*

Abbreviations: CI=confidence interval; GMT=geometric mean titer; OPA=opsonophagocytic activity

* Identifies statistically significant differences

Source: VAC-056 Final Statistical Report Table 14.2.2-2.2

Finally, a booster response was demonstrated for all 10 serotypes in both vaccine groups (data not shown). Post-booster IgG GMCs were significantly higher in the PNEUMOSIL group for 8 serotypes (1, 5, 6A, 6B, 7F, 14, 19A, 23F), and significantly higher in the Synflorix group for 2 serotypes (9V, 19F) (Table 10).

Table 10. Booster Response: Treatment Group IgG GMCs and Treatment-Group GMC Ratios (VAC-056)

Serotype	n	PNEUMOSIL (N=425)		Synflorix (N=209)		Treatment group comparison: PNEUMOSIL/Synflorix		
		GMC	(95% CI)	n	GMC	(95% CI)	GMC Ratio	(95% CI)
Type 1	425	5.73	(5.27 – 6.22)	209	2.45	(2.16 – 2.78)	2.34	(2.02 – 2.71)
Type 5	425	1.31	(1.21 – 1.41)	208	0.83	(0.75 – 0.92)	1.57	(1.38 – 1.79)
Type 6A	424	4.87	(4.41 – 5.39)	209	0.42	(0.35 – 0.49)	11.6	(9.67 – 14.0)
Type 6B	423	8.33	(7.71 – 9.00)	209	4.42	(3.98 – 4.90)	1.89	(1.65 – 2.15)
Type 7F	425	6.37	(5.88 – 6.90)	209	4.06	(3.65 – 4.50)	1.57	(1.37 – 1.80)
Type 9V	424	1.81	(1.67 – 1.95)	209	2.07	(1.87 – 2.30)	0.87	(0.76 – 0.99)
Type 14	420	6.85	(6.09 – 7.70)	204	4.62	(3.88 – 5.50)	1.48	(1.21 – 1.82)
Type 19A	423	3.97	(3.64 – 4.34)	205	0.94	(0.78 – 1.14)	4.22	(3.52 – 5.06)
Type 19F	416	6.16	(5.68 – 6.68)	204	9.70	(8.68 – 10.83)	0.63	(0.55 – 0.73)
Type 23F	425	4.08	(3.72 – 4.47)	209	2.13	(1.88 – 2.42)	1.91	(1.63 – 2.24)

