12.1. Sample Size Considerations

Previous clinical studies have provided the necessary immunogenicity, safety, and tolerability data to support WHO pre-qualification (PQ) of PNEUMOSIL. The current study is intended to provide additional data to assist WHO-PQ and regulatory authorities in making recommendations regarding the immunogenicity and safety of PNEUMOSIL when delivered in a 2+1 dosing schedule. Since there are no hypothesis tests specified in this supportive study, sample size considerations are based on expected

precision of immunogenicity-related parameter estimates, rates of AEs, and descriptive comparisons between treatment groups in these measures, which are considered sufficient by the study team to generate actionable data by regulatory authorities.

All sample size calculations assume the use of descriptive 95% CIs (both for treatment group-specific measures and differences between groups), with no adjustment for multiple comparisons. Unless otherwise noted, asymptotic Wald-type CIs will be used when describing proportions, and asymptotic likelihood Score-type intervals for differences in proportions. Log-normality will be assumed when computing CIs for GMCs, GMTs, and their ratios between groups.

Primary Immunogenicity Objective:

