With a sample size of 220 per group (up to 10% of whom may not be evaluable), the half-width of 95% CIs for serum IgG response rates ($\text{IgG} \geq 0.35 \mu\text{g/mL}$ or $\text{IgG} \geq 1.0 \mu\text{g/mL}$) will be no more than 0.07, and the half-width of 95% CIs for differences in proportions should not exceed 0.10.

Precision of Serum OPA Titer Response Rates and Differences in Rates

With a sample size of 50 per group (and no more than 10% excluded), the half-width of 95% CIs for OPA response rates (titer $\geq 1:8$) will be no more than 0.15, and the half-width of 95% CIs for differences in proportions responding (PNEUMOSIL versus a comparator) should not exceed 0.21.

Precision of OPA GMTs and GMT ratios

The VAC-056 study observed CV values that ranged from 0.97 to 2.11 for serotype-specific OPA titers measured 4 weeks after a booster dose of PNEUMOSIL in infants. Assuming the CVs for all 10 PNEUMOSIL serotypes in the current study are at most 2.11 at any given secondary analysis time point, then the lower and upper 95% confidence bounds for each GMT are expected to be at most 32% below and 48% above the observed GMT based on the study size of 50 per group (assuming no more than 10% of subjects are not evaluable due to loss to follow-up or other exclusions). For example, if the observed serotype-specific GMT = 100, then the 95% CI is expected to be no wider than (68, 148). Similarly, the expected lower and upper 95% confidence bounds for descriptive GMT ratios

(PNEUMOSIL versus either comparator) are expected to be no more than 42% below and 73% above the ratio. For example, if the observed GMT ratio equals 1, then the 95% CI is expected to be no wider than (0.58, 1.73), so long as the CV in the comparison group does not exceed 2.11.

Safety

With a sample size of 220 infants vaccinated per group, there is an 89% chance of observing at least 1 safety endpoint (e.g., a solicited AE) which occurs with probability 0.01 or more; if no events of a specific classification occur then the 95% upper confidence bound for the event rate will be 0.017.

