3.2.3. Secondary Immunogenicity Objectives

The precision of IgG GMCs 4 weeks post completion of primary vaccination (V4) is expected to be as for the primary objective under the same assumptions about CV of serotype-specific IgGs and follow-up rates as previously described. The expected precision of other secondary immunogenicity objectives (IgG response rates, OPA response rates, and OPA GMTs) are as follows:

With a sample size of 220 per group (up to 10% of whom may not be evaluable), the half-width of 95% CIs for serum IgG response rates ($\text{IgG} \geq 0.35 \mu\text{g/mL}$ or $\text{IgG} \geq 1.0 \mu\text{g/mL}$) will be no more than 0.07, and the half-width of 95% CIs for differences in proportions should not exceed 0.10.

With a sample size of 50 per group (and no more than 10% excluded), the half-width of 95% CIs for OPA response rates (titer ≥ 8) will be no more than 0.15, and the half-width of 95% CIs for differences in proportions responding (PNEUMOSIL versus a comparator) should not exceed 0.21.

The VAC-056 study observed CV values that ranged from 0.97 to 2.11 for serotype-specific OPA titers measured 4 weeks after a booster dose of PNEUMOSIL in infants. Assuming the CVs for all 10 PNEUMOSIL serotypes in the current study are at most 2.11 at V4 and V6, the lower and upper 95% confidence bounds for each GMT are expected to be at most 32% below and 48% above the observed GMT based on the study size of 50 per group (assuming no more than 10% of subjects are not evaluable due to loss to follow-up or other exclusions). For example, if the observed serotype-specific GMT = 100, then the 95% CI is expected to be no wider than (68, 148). Similarly, the expected lower and upper 95% confidence bounds for descriptive GMT ratios (PNEUMOSIL versus either comparator) are expected to be no more than 42% below and 73% above the ratio. For example, if the observed GMT ratio equals 1, then the 95% CI is expected to be no wider than (0.58, 1.73), so long as the CV in the comparison group does not exceed 2.11.

Due to positive within-subject correlation among subjects contributing both V4 and V6 data, the precision of within-group booster-effects (ratios of GMCs and GMTs post-booster versus post-primary series) is expected to be at least as high as that of the between-group contrasts at V4 or V6 described above, under similar assumptions about CV and the percentage of evaluable subjects.

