3.5. Selection of OPA Specimens

Prior to the interim analysis of primary series immunogenicity data, the PI provided the ratio of subject enrolments per field site expected to be achieved at the completion of the trial. Based on this ratio, the independent statistician selected (based on order of entry into the study, not randomly) the first 27 subjects with evaluable V4 specimens in each treatment group from the Brikama field site, and the first 23 subjects with evaluable V4 specimens in each treatment group from the Bundung site, such that a total of 50 subjects per group were selected for OPA analysis proportional to the enrolment total in each site. Selected subjects who did not complete V5 per protocol were later replaced with new subjects from the same field site and treatment group to contribute V5 and V6 OPA data (with replacements also selected in order of enrolment date, not randomly). If more than 10% of subjects fail to contribute evaluable results at a given visit, then additional subjects may have their specimens analysed to help ensure at least 45/group contribute to each secondary functional antibody analysis timepoint. The PATH Clinical Lead will make this determination in blind review of data once the availability of OPA results has been determined for all selected subjects.

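### Stated OPA precision at V4 rests on a post-booster CV ceiling of 2.11 that the protocol's own post-primary VAC-056 data exceed, clearly for 6B, 9V, 14 and 19A

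*Protocol*

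**What the plan says.** Protocol 12.1 bases sample size on expected precision, because no hypothesis tests are specified, and describes the resulting precision as figures "which are considered sufficient by the study team to generate actionable data by regulatory authorities".

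For OPA titers the input is this: "The VAC-056 study observed CV values that ranged from 0.97 to 2.11 for serotype-specific OPA titers measured 4 weeks after a booster dose". The protocol then carries the upper end to all secondary time points ("Assuming the CVs for all 10 PNEUMOSIL serotypes in the current study are at most 2.11 at any given secondary analysis time point"). The SAP names two visits: "Assuming the CVs for all 10 PNEUMOSIL serotypes in the current study are at most 2.11 at V4 and V6".

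With 50 per group and up to 10% not evaluable, both documents state that 95% limits will be at most 32% below and 48% above a GMT, and at most 42% below and 73% above a GMT ratio. The ratio statement carries a proviso: "so long as the CV in the comparison group does not exceed 2.11". SAP 3.5 uses 45 per group as its working floor: "additional subjects may have their specimens analysed to help ensure at least 45/group contribute to each secondary functional antibody analysis timepoint".

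Neither document gives a post-primary OPA CV, says why a post-booster ceiling should hold at V4, or says how the CVs were calculated.

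**The concern.** V4 is four weeks after the primary series, not after a booster. Protocol 1.8.2 prints VAC-056 post-primary OPA results in Table 9 with sample sizes and confidence limits, so the log-scale spread at the matching time point can be recovered. If it exceeds the ceiling, the V4 bounds are too narrow for the affected serotypes.

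At stake is the precision rationale for the V4 OPA GMTs and GMT ratios in secondary objective 4. In a descriptive trial, that rationale takes the place of a power calculation.

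**Working it through.** **Inputs.** CV 2.11 and 45 evaluable of 50 (Protocol 12.1, SAP 3.2.3); log-normality (Protocol 12.1); group sizes and 95% intervals from Protocol Tables 9 and 11.

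**Formulas.**
- SD of ln titer from a CV: √ln(1 + CV²). Inverse: CV = √(exp(SD²) − 1).
- SD from a printed interval: ln(upper/lower) × √n / (2 × t₀.₉₇₅,ₙ₋₁).
- GMT limits: exp(± t₀.₉₇₅,ₙ₋₁ × SD/√n).
- Ratio limits: exp(± t₀.₉₇₅,₂ₙ₋₂ × √((SD₁² + SD₂²)/n)).
- 95% limits for an SD come from the chi-square distribution, then converted to CV.

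**Plan's figures reproduced.** SD = √ln(1 + 2.11²) = 1.302.
- GMT, n = 45: exp(± 2.015 × 1.302/√45) = 0.676 to 1.479, that is 32/48.
- Ratio: exp(± 1.987 × 1.302 × √(2/45)) = 0.579 to 1.726, that is 42/73.

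The arithmetic is right.

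**V4 spread: one example.** For 9V, n = 242 and the Table 9 interval is "113.36 – 177.16". SD = ln(177.16/113.36) × √242 / (2 × 1.970) = 1.763, so CV = 4.62. At n = 45 the GMT factor is exp(± 2.015 × 1.763/√45) = 0.589 to 1.698. Type 14 (n = 244, "816.53 – 1272.52") gives almost the same.

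**All ten serotypes** (percent below/above at 45 per group; ratio uses both arms' Table 9 SDs):

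| Serotype | PNEUMOSIL SD | CV (95% limits) | GMT | Synflorix SD | Ratio vs Synflorix |
|---|---|---|---|---|---|
| Plan | 1.302 | 2.11 | 32/48 | 1.302 | 42/73 |
| 1 | 1.414 | 2.53 (2.10–3.18) | 34.6/52.9 | 1.460 | 45.2/82.6 |
| 5 | 1.136 | 1.62 | 28.9/40.7 | 1.277 | 39.7/65.9 |
| 6A | 1.370 | 2.35 (1.97–2.93) | 33.7/50.9 | 1.513 | 45.4/83.1 |
| 6B | 1.603 | 3.48 (2.78–4.60) | 38.2/61.9 | 1.963 | 52.8/111.9 |
| 7F | 1.027 | 1.37 | 26.5/36.1 | 1.048 | 35.2/54.4 |
| 9V | 1.763 | 4.62 (3.57–6.43) | 41.1/69.8 | 1.209 | 46.9/88.4 |
| 14 | 1.759 | 4.59 (3.55–6.37) | 41.1/69.6 | 1.813 | 52.7/111.3 |
| 19A | 1.616 | 3.55 (2.84–4.71) | 38.5/62.5 | 1.467 | 47.6/90.9 |
| 19F | 1.221 | 1.85 | 30.7/44.3 | 1.057 | 38.0/61.3 |
| 23F | 1.333 | 2.22 (1.87–2.74) | 33.0/49.3 | 1.979 | 50.7/102.8 |

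The lower CV limit is above 2.11 for exactly four serotypes: 6B, 9V, 14 and 19A.

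**Proviso met.** With the comparator SD fixed at 1.302, the ratio at n = 45 is 45.8/84.4 (6B), 47.8/91.4 (9V), 47.7/91.3 (14) and 45.9/84.9 (19A).

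**All 50 evaluable.** The GMT intervals for these four are still about 37/58 (6B, 19A) and 39/65 (9V, 14).

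**V6 check from Table 11.** PNEUMOSIL log-normal CVs run from 1.54 (7F) to 2.63 (14), not 0.97 to 2.11. Seven point estimates exceed 2.11: 1 (2.35), 5 (2.32), 6A (2.34), 9V (2.39), 14 (2.63), 19A (2.36) and 23F (2.14). No lower 95% limit does; the highest is 1.97, for type 14. At n = 45, GMT intervals run from 28/39 (7F) to 35/54 (14), with 1, 5, 6A, 9V and 19A near 34/51. Ratios against Synflorix run from 36/57 (7F) to 50/100 (14) for shared serotypes. They reach 54/120 for 19A and 59/146 for 6A, neither of which Synflorix contains (Protocol 5.2.1).

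**The case against.** The best defence is that the statements are conditional and true as written: if every CV is at most 2.11, the widths follow. That stands as logic, but a planning condition needs support, and Table 9 contradicts this one for four serotypes. The comparator proviso does not help, because the GMT bound involves no comparator and the ratio bound fails for those four even when the proviso is met.

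A second defence is that Table 9 follows three primary doses at 6, 10 and 14 weeks, whereas V4 here follows two doses at 6 and 14 weeks. That is a real limit on the substitute figures. The plan's own source, titers after a booster given on top of that three-dose series, is no closer to V4.

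A third is that the consequence is small, and this largely stands. There is no test or decision rule tied to interval width, and reported intervals will use observed data (SAP 5.1). Objective 4 also includes response rates, whose half-widths of 0.15 and 0.21 do not depend on CV. The 45 per group in SAP 3.5 is 10% off 50, not a CV-derived number.

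A reader might also infer that the time point is the whole explanation, so that 2.11 could safely be kept at V6. Table 11 does not support that: seven point estimates exceed it there too, though within sampling error, and the widest Synflorix ratios are post-booster. Nor do the documents establish that the quoted CVs are raw-scale values put into a log-normal formula. That would fit the mismatch with Table 11, but the calculation is not described.

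**Conclusion.** The concern holds for V4 OPA precision. The stated maxima of 32/48 (GMT) and 42/73 (ratio) for all ten serotypes are contradicted by the protocol's own post-primary data for 6B, 9V, 14 and 19A. Expect GMT intervals of about 38/62 to 41/70 for these. Expect ratios of about 46/84 to 48/91 with the comparator at the ceiling, and up to about 53/112 against Synflorix.

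Types 1, 6A and 23F exceed the GMT bound only marginally, with CV limits that include 2.11; 5, 7F and 19F are within both bounds.

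This assumes that VAC-056 three-dose post-primary variability transfers to the 2+1 schedule. The documents give nothing from which to derive Prevenar 13 post-primary variability or V5 variability for OPA.

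It would be too strong to conclude that the trial is underpowered or that the OPA subset must grow. Matching the stated GMT width would take about 67 (6B), 68 (19A), 80 (14) or 81 (9V) evaluable sera per group. That shows the size of the gap; it is not a requirement, since no decision depends on the width. Error control, safety precision and response-rate precision are unaffected.

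**What to change.** In SAP 3.2.3, and in Protocol 12.1 at its next amendment, replace the single OPA ceiling with precision by time point, given as expected values at 45 evaluable per group:

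- **V4 (Table 9 SDs):** PNEUMOSIL GMT about 27/36 (7F) to 41/70 (9V, 14); ratio to Synflorix about 35/54 (7F) to 53/112 (6B).
- **V6 (Table 11 SDs):** PNEUMOSIL GMT about 28/39 (7F) to 35/54 (14), with 1, 5, 6A, 9V and 19A about 34/51; ratio to Synflorix about 36/57 (7F) to 50/100 (14) for shared serotypes, and about 54/120 (19A) and 59/146 (6A) for the two not in Synflorix.

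Do not keep 2.11 as a log-scale maximum at V6. State the scale on which the quoted 0.97 to 2.11 was computed. State that transfer from a three-dose primary series to 2+1 is assumed, and that Prevenar 13 and V5 variability are unknown.

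Enrolment, OPA selection and analysis stay as they are. The cost is a few sentences and less favourable stated precision. Because protocol modifications go to the authorities for review (Protocol Section 14), the SAP is the place to start.

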12.2. Analysis Populations

The Enrolled Population will include all screened subjects who provide informed consent, regardless of whether the subject is randomized to receive a study treatment. This population will be used to account fully for subject disposition, starting with the informed consent.

The Safety Population will include all subjects who were randomized, received a vaccination, and provided at least some post-vaccination safety data; all treated subjects are expected to contribute to this population. Treatment groups for safety analyses will be assigned according to the actual treatment received at Visit 1. This population will serve as the primary analysis population for demographics and study disposition as well as safety.

The Full Immunogenicity Population (FIP) includes subjects in the enrolled population who were randomized, received a study vaccination, and have one or more post-vaccination immunogenicity measurement(s). Analysis will be according to the treatment received by each subject, even if different from that to which the subject was randomized.

The Primary Per Protocol Immunogenicity (PP_IMM) Population will include all subjects in the FIP who received all 3 study vaccine doses (including booster) and have post-booster immunogenicity measurements. The Secondary PP_IMM Population (used for the analysis of Visit 4 data) will include all subjects who received both primary series doses and contribute immunogenicity measurement(s) 4 weeks post primary series.

Any exclusion from these populations (e.g., due to major protocol deviations that could potentially interfere with immune responses or the interpretability of findings) will be established in blind review of data by the Clinical Lead alone. To minimize the possibility of unintentional un-blinding, participant identifiers will be masked by the statistician providing relevant data listings on protocol deviations.

12.3. Handling of Dropouts or Missing Data

Immunogenicity values falling below the lower limit of quantitation or the lower limit of detection will be assigned a value of $\frac{1}{2}$ the applicable limit. Values above an upper limit of quantification will be assigned the upper limit. Rules for imputing incomplete AE onset dates will be documented in the SAP. No other missing data imputation is planned for the study. If any is necessary, however, appropriate imputation rules will be established in blind review.

12.4. Multiple Comparisons/Multiplicity

There will be no type I error control of multiple comparisons in this descriptive study. All tests will be two-sided and conducted at the 0.05 significance level, and a coverage level of 95% will be used for all confidence intervals.

12.5. Timing of Interim and Final Analyses

An interim analysis of immunogenicity objectives through the end of V4 will occur when all subjects have completed V4, at which time the CRO statisticians responsible for the analysis will be unblinded. The Sponsor, Principal Investigator, site team, other CRO personnel and laboratory staff performing immunogenicity assays, will remain blinded until the completion of the trial. The final analysis of other endpoints will be conducted when all subjects have completed V6 and the database is locked.

12.6. Assessment of Study Populations

Disposition, demographic, and other baseline characteristics will be provided for the Safety and PP_IMM Populations.

12.6.1. Participant Disposition

The numbers of participants enrolled, participants enrolled but not randomized (and reason), participants who withdraw early (and reason), and participants who complete the study will be summarized using descriptive statistics.

12.6.2. Demographic and Other Baseline Characteristics

Demographic and baseline characteristics will be summarized using frequencies and percentages for categorical data, and means, standard deviations, medians, and range for continuous variables. Data listings will be sorted by treatment group and subject ID number. Tabular summaries will be presented by subject ID.

12.7. Immunogenicity Analyses

12.7.1.1. Primary Objective

The primary immunogenicity objective is to evaluate serum IgG antibody responses (GMCs) to the 10 serotypes in PNEUMOSIL, alone and in comparison to antibody responses to these serotypes induced by Prevenar 13 and Synflorix at 4 weeks post booster dose. Serum IgG GMCs will be reported by PNEUMOSIL serotype and treatment group, together with 95% CIs. For each serotype, GMC ratios (PNEUMOSIL vs. each comparator) and associated 95% CIs for the GMC ratio will be reported based on log-linear models, with no adjustment for multiple comparisons.

12.7.2. Secondary Objectives

Secondary Objective 1 is to evaluate – in a subset of subjects in the Primary PP_IMM Population – functional antibody responses to the 10 serotypes in PNEUMOSIL as measured by OPA at 4 weeks post the booster dose. Serotype-specific OPA GMTs will be reported by PNEUMOSIL serotype and treatment group, together with 95% CIs. Serotype-specific GMT ratios (PNEUMOSIL versus each comparator) and associated 95% CIs will be reported based on log-linear models.

Secondary Objective 2 is to evaluate the proportion of subjects with serotype-specific serum IgG concentrations $\geq 0.35 \mu\text{g/mL}$, serum IgG concentrations $\geq 1.0 \mu\text{g/mL}$, and serum OPA titers $\geq 1:8$ at 4 weeks post the booster dose by treatment group, together with 95% CIs. Serotype-specific differences in response rates (PNEUMOSIL vs. each comparator) will be reported with 95% CIs.

Secondary Objective 3 is to evaluate serum IgG antibody responses to the 10 serotypes in PNEUMOSIL at 4 weeks post 2-dose primary series. The percentage of responders (subjects with serum IgG concentrations $\geq 0.35 \mu\text{g/mL}$) will be reported by PNEUMOSIL serotype and treatment group, together with 95% CIs. Differences in response percentages (PNEUMOSIL vs. each comparator) will be reported with 95% CIs, with no adjustment for multiple comparisons. Serum IgG GMCs will be reported by PNEUMOSIL serotype and treatment group, together with 95% CIs. For each serotype, GMC ratios (PNEUMOSIL vs. each comparator) and associated 95% CIs for the GMC ratio will be reported based on log-linear models.

Secondary Objective 4 is to evaluate – in a subset of subjects in the Secondary PP_IMM Population – functional antibody responses to the 10 serotypes in PNEUMOSIL as measured by OPA at 4 weeks post the 2-dose primary series. The proportion of subjects with serotype-specific serum OPA titers $\geq 1:8$ and GMTs 4 weeks post dose 2 will be reported by PNEUMOSIL serotype and treatment group, together with 95% CIs. Serotype-specific differences in response percentages (PNEUMOSIL vs. each comparator) and GMT ratios will be reported with 95% CIs based on log-linear models.

Secondary Objective 5 is to evaluate the persistence of serum IgG antibody responses to the 10 serotypes in PNEUMOSIL at 9-18 months of age, prior to the booster dose. The percentage of responders (IgG $0.35 \mu\text{g/mL}$) and GMCs will be reported by PNEUMOSIL serotype and treatment group, together with 95% CIs. Serotype-specific differences in response rates (PNEUMOSIL vs. each comparator) and GMC ratios will be reported with 95% CIs.

Secondary Objective 6 is to evaluate – in a subset of subjects in the Primary PP_IMM Population – the persistence of functional antibody responses to the 10 serotypes in PNEUMOSIL as measured by OPA at 9-18 months of age, prior to the booster dose. The proportion of subjects with serotype-specific serum OPA titers $\geq 1:8$ and GMTs will be reported by PNEUMOSIL serotype and treatment group, together with 95% CIs. Serotype-specific differences in response percentages (PNEUMOSIL vs. each comparator) and GMT ratios will be reported with 95% CIs.

Secondary Objective 7 is to evaluate booster responses (serum IgG concentrations and functional responses) from 4 weeks after the primary series (V4) to 4 weeks post booster dose (V6). For each PNEUMOSIL serotype, the ratio of post-booster to post-primary series IgG GMCs and OPA GMTs will be reported by treatment group with 95% CIs, restricted to subjects who provide response data at both V4 and V6.

In addition to the summary measures of immunogenicity responses described above for each of the primary and secondary objectives, reverse cumulative IgG concentration and OPA titer distribution curves will be presented by serotype and treatment group.

